3.4.4. Post Discharge

- Patients will have CBC with differential and Chem 20 drawn weekly until values are less than or equal to grade 2 or baseline. This may be done through the patient's referring physician with the results faxed to [name] or his designee.

- Patients will return to clinic approximately 4-6 weeks following surgery for their 1st post operative visit. Subsequent follow up is detailed in section 3.9.

3.5. Systemic Chemotherapy Therapy

3.5.1. Guidelines

Patients who randomize to receive systemic chemotherapy alone (SA) will begin treatment within 14 days of randomization; patients who undergo palliative gastrectomy will begin chemotherapy within 6-8 weeks of randomization. Patients who randomize to surgery plus chemotherapy (GYMS) will begin treatment approximately 6-8 weeks following surgery (24 weeks for patients requiring sequential thoracic and abdominal surgery). **Note:** patients must meet eligibility requirements prior to beginning chemotherapy. Patients who do not recover from the surgical procedure within the stated timeframe will be removed from treatment and followed for survival.

Systemic therapy may be administered by the patient's local oncologist in collaboration with the PI or at the NCI by the Medical Oncology Branch. Systemic therapy will follow the guidelines for the FOLFOXIRI regimen⁷⁷. Chemotherapy and supportive care will be administered in accordance with each institution's policies for the administration of chemotherapeutic agents.

During treatment, the treating oncologist will be asked to fax the following information (Appendix 8) to the research nurse (noted below) at the conclusion of every other cycle (4 weeks):

- chemotherapy administration sheets including dose reductions and reason for dose reduction
- laboratory test results
- other clinically relevant information

The patient will be asked to maintain a diary to be faxed to the research nurse every 4 weeks:

[name] RN
[contact]

All systemic chemotherapy will be administered based on actual body weight if within 20% above or below the ideal body weight. If actual weight is not within 20% of ideal body weight, then ideal body weight will be used to calculate systemic chemotherapy doses.

Ideal body weight will be calculated based upon the following formula:

$$\begin{aligned} \text{IBW (male, in kg)} &= \{(\text{Height in inches} - 60 \} \times 2.3 \} + 50 \\ \text{IBW (female, in kg)} &= \{(\text{Height in inches} - 60 \} \times 2.3 \} + 45.5 \end{aligned}$$

3.5.2. Treatment Schedule FOLFOXIRI

[figure not shown]
Systemic chemotherapy will be administered every other week (one treatment every 14 days), and repeated for 12 cycles (approximately 6 months). Patients in the systemic chemotherapy alone (SA) arm who are responding may continue chemotherapy beyond 12 cycles at the discretion of the PI. Refer to Section 8 for further administration guidelines.

Day 1: Irinotecan will be administered IV over 90 minutes followed by leucovorin IV and oxaliplatin IV given concomitantly over 2 hours, followed by 5-FU given via continuous infusion (CIV) over 48 hours.

Dose Level

Agent	Starting Dose	Dose level -1 (25% reduction)	Dose level -2 (50% reduction)
Irinotecan	165mg/ m ² IV	123 / m ² IV	82 /m ² IV
Leucovorin	200 mg/m ² IV	200 m ² IV	200 mg/m ² IV
Oxaliplatin	85 mg/m ² IV	63 mg/m ² IV	42 mg/m ² IV
5-FU	3200 mg/m ² CIV	2400 mg/m ² CIV	1600 mg/m ² CIV

Cycle 1 Week 1

3.5.3. Treatment Modifications FOLFOXIRI

Treatment will be continued for up to 12 cycles (4 cycles = 1 course) unless one of the following events occur: disease progression, unacceptable adverse effects, or withdrawal of patient consent. Dose modification will be based on toxicity profiles and adverse effects based upon the National Cancer Institute Common Terminology Criteria for Adverse Events (CTCAE version 3.0).

The dose levels for oxaliplatin, irinotecan, leucovorin and 5-FU are noted above; the dose modification table is attached as Appendix 4.

NOTE: Patients for whom peripheral neuropathy would pose significant hardship (e.g., musicians, jewelers, dentists) may receive the standard FOLFIRI regimen as noted below.

FOLFIRI			
Agent	Starting Dose	Dose level -1 (25% reduction)	Dose level -2 - 50% reduction
Irinotecan	180 mg/ m ² IV	150 / m ² IV	120 /m ² IV
Leucovorin	200 mg/m ² IV	200 m ² IV	200 mg/m ² IV
5-FU bolus	400 mg/m ² IV	320 mg/m ² IV	240 mg/m ² IV
5-FU infusion (over 46 hours)	2400 mg/m ² CIV	2000 mg/m ² CIV	1600 mg/m ² CIV

Day 1: Irinotecan will be administered IV over 90 minutes followed by leucovorin IV over 2 hours followed by 5-FU bolus injection, followed by 5-FU given via continuous infusion (CIV) over 46 hours. Dose reductions will follow appendix 4; all evaluations will follow the same schedule as outlined for FOLFOXIRI.

3.6. Treatment Evaluation During Chemotherapy:

- Laboratory evaluation weekly or according to the standards of the treating physician, to include: CBC with differential and Chem 20: (Sodium (Na), Potassium (K), Chloride (Cl), Total CO₂ (bicarbonate), Creatinine, Glucose, Urea nitrogen (BUN), Albumin, Calcium total, Magnesium total (Mg), Inorganic Phosphorus, Alkaline Phosphatase, ALT/GPT, AST/GOT, Total Bilirubin, Direct Bilirubin, LD, Total Protein, Total CK, Uric Acid).
- Physical examination and toxicity assessment every 2 weeks or according to the standards of the treating physician

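### The FOLFIRI dose-level headings in section 3.5.3 (25% and 50% reductions) do not match the mg/m² doses beneath them, and Appendix 4 does not say which governs

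*Combined protocol and SAP*

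**What the plan says.** Both arms are to receive FOLFOXIRI. Section 3.5.3 makes an exception for patients to whom peripheral neuropathy would be a particular hardship: they may be given FOLFIRI, for which it prints a separate table. The first reduced column is headed "Dose level -1 (25% reduction" and the second "Dose level -2 - 50% reduction". Beneath these headings the doses at start, level -1 and level -2, in mg/m², are:

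- irinotecan 180, 150, 120
- leucovorin 200, 200, 200
- 5-FU bolus 400, 320, 240
- 5-FU infusion 2400, 2000, 1600

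For how these levels are applied, the section says "Dose reductions will follow appendix 4". Appendix 4 is titled for FOLFOXIRI. It instructs the reader to maintain the level, drop one or two levels, or discontinue, and it contains no mg/m² values and no percentages.

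The FOLFOXIRI table in section 3.5.2 uses the same scheme; its second reduced column is headed "Dose level -2 (50% reduction".

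**The concern.** A dose-level table is an operative instruction for giving cytotoxic drugs. Here the heading and the cells give different sizes of reduction for every FOLFIRI agent that is reduced. Section 3 prefers that patients on systemic therapy alone be treated by their home oncologist, and section 3.5.1 allows local administration under each institution's own policies. Some prescribers will therefore be outside the study centre, and a percentage in a column heading is something a prescriber can act on.

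The rule that should settle the matter does not. Appendix 4 counts levels without defining them, and it has a single 5-FU column although FOLFIRI has both a bolus and an infusion. The sentence in section 3.5.3 that says where the dose levels are found stands before the FOLFIRI table and lists oxaliplatin, so it points back to the FOLFOXIRI table.

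What is at stake is the dose given after toxicity to the few patients concerned.

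**Working it through.** **Inputs.** Doses and headings are from the tables in sections 3.5.2 (FOLFOXIRI) and 3.5.3 (FOLFIRI). Leucovorin is held at 200 mg/m² at every level in both tables and is left out.

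**Formula.** Percentage reduction = 100 × (1 − reduced dose / starting dose).

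**Step 1. Reproduce the headings where they work (FOLFOXIRI).**

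| Agent | Start / -1 / -2 | Level -1 | Level -2 |
|---|---|---|---|
| Irinotecan | 165 / 123 / 82 | 1 − 123/165 = 25.5% | 1 − 82/165 = 50.3% |
| Oxaliplatin | 85 / 63 / 42 | 1 − 63/85 = 25.9% | 1 − 42/85 = 50.6% |
| 5-FU | 3200 / 2400 / 1600 | 1 − 2400/3200 = 25.0% | 1 − 1600/3200 = 50.0% |

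The headings hold to rounding, so they are meant as percentages of the starting dose.

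**Step 2. Same arithmetic for FOLFIRI.**

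| Agent | Start / -1 / -2 | Level -1 | Level -2 |
|---|---|---|---|
| Irinotecan | 180 / 150 / 120 | 1 − 150/180 = 16.7% | 1 − 120/180 = 33.3% |
| 5-FU bolus | 400 / 320 / 240 | 1 − 320/400 = 20.0% | 1 − 240/400 = 40.0% |
| 5-FU infusion | 2400 / 2000 / 1600 | 1 − 2000/2400 = 16.7% | 1 − 1600/2400 = 33.3% |

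No reduced agent meets either heading.

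**Step 3. Try other readings.**

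- Level -2 relative to level -1: irinotecan 1 − 120/150 = 20%; bolus 1 − 240/320 = 25%; infusion 1 − 1600/2000 = 20%. None is 50%.
- Bolus and infusion added together, 2800 / 2320 / 1840: 1 − 2320/2800 = 17.1% and 1 − 1840/2800 = 34.3%. Neither is 25% or 50%.

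**Step 4. Size of the gap.** Label-implied dose = start × 0.75 at level -1 and start × 0.50 at level -2. Excess = tabulated / implied − 1.

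| Agent | Implied -1 / -2 | Tabulated -1 / -2 | Excess at -1 | Excess at -2 |
|---|---|---|---|---|
| Irinotecan | 135 / 90 | 150 / 120 | 11% | 33% |
| 5-FU bolus | 300 / 200 | 320 / 240 | 7% | 20% |
| 5-FU infusion | 1800 / 1200 | 2000 / 1600 | 11% | 33% |

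The implied doses only measure the conflict. They appear nowhere in the protocol and are not proposed.

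**The case against.** The best answer is that this is a mislabelled heading and nothing more. Each FOLFIRI level has one printed mg/m² dose per agent, and Appendix 4 sends the reader to a level, hence to a column with explicit doses. A different dose arises only if someone ignores the cell and calculates from the heading. That stands, and it limits the point to what could happen. It does not remove the point, because no text gives the cell precedence over the heading.

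Three stronger readings are tempting, and the documents do not support them.

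- **Each reduced patient has two prescribed doses.** Only one dose per level is printed; the other has to be derived from the label.
- **Any patient with grade 3-4 toxicity would be dosed differently.** Only patients on FOLFIRI are concerned, and Appendix 4 maintains all doses for grade 3 neutropenia and for grade 3-4 anemia. It maintains 5-FU for every listed grade of neutropenia and thrombocytopenia, and irinotecan for mucositis. A direct two-level drop is listed only for ten or more stools a day above baseline, grade 4 mucositis (5-FU only) and grade 4 other non-hematologic toxicity.
- **The secondary objective on chemotherapy dosing is compromised.** A level recorded without a dose would mean different percentages under the two regimens. But section 3.5.1 has administration sheets sent to the research nurse, and section 7.2.1 has all reductions and their reasons captured, so the dose given should be recoverable. Both arms use the same FOLFIRI table, and no between-arm bias is shown.

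**Conclusion.** The inconsistency is real and sits in the current text. The FOLFIRI headings state 25% and 50%; the doses deliver 16.7% and 33.3% for irinotecan and infusional 5-FU, and 20% and 40% for bolus 5-FU. The tabulated doses exceed the label-implied ones by 7-11% at level -1 and 20-33% at level -2.

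This takes the headings as percentages of the starting dose, which the FOLFOXIRI table bears out. The practical consequence assumes that some prescriber works from the heading. The protocol does not say how many patients will receive FOLFIRI or need a reduction on it, so the number exposed cannot be estimated. The primary survival analysis is unaffected.

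A reader might infer that the headings were carried over from the FOLFOXIRI table and that the cells are therefore right. The documents do not say so, and the arithmetic cannot decide it. The correction is worth making because the table directs cytotoxic dosing.

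**What to change.** The sponsor's clinical team should decide what each FOLFIRI dose level is meant to be, then make the percentage headings and the mg/m² values in section 3.5.3 agree. In the same change, add a sentence stating that for FOLFIRI patients Appendix 4's dose levels refer to this table, and that its 5-FU column covers the bolus, the infusion or both, as the team intends.

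The cost is one table correction and one sentence in the next amendment. Sample size, data collection and analysis do not change.

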3.7. Evaluation of Response and QOL Assessment

- CT scan of the chest/abdomen/pelvis will be performed within 4 weeks prior to the first chemotherapy treatment and then every 8 weeks (+/- 1 week) during chemotherapy (at the end of each course).
- Response will be determined using RECIST criteria
- Quality of Life Questionnaires as described in Section 3.11.

3.8. Off Treatment Criteria

- Completion of systemic chemotherapy regimen
- Voluntary withdrawal from treatment
- Inability to follow the treatment regimen
- Unacceptable toxicity
- Radiographic or clinical disease progression
- Unwilling or unable to undergo surgical resection for progressive disease
- If the physician deems it is in the patient's best interest not to receive further treatment
- Completion of chemotherapy

3.9. Post Treatment Follow up (Both Arms)

Patients will be evaluated every 12 weeks (+/- 2 weeks) for the first 2 years, following completion of chemotherapy, every 6 months for the next 3 years and yearly thereafter. At any stage between these follow-ups additional evaluations will be conducted as clinically indicated. At each evaluation patients will undergo:

- Physical examination
- Laboratory tests to include CBC with differential and CHEM 20
- Tumor markers as appropriate
- CT scan of the chest, abdomen and pelvis and other imaging as appropriate
- Completion of QOL measures

Patients who are unwilling or unable to return for follow up evaluation will be followed by phone contact. The following information may be obtained:

- Summary of treatment received since the previous contact
- Estimation of ECOG status
- Request for imaging studies, physical exam and laboratory reports to be sent to the PI

Note: The CT of chest/abdomen and pelvis, done within 2 weeks of randomization, will be used as the base line study for assessment of disease progression. In special cases MRI-L (liver MRI) will be used to assess liver disease or PET scan when indicated.

Patients randomized to the GYMS arm who progress during the follow up period will be offered further debulking/metastasectomy if deemed in the best interest of the patient. No additional chemotherapy will be given as a part of this protocol; however, patients may be referred to other NCI treatment protocols or back to their treating oncologist.

3.10. Off Study Criteria

- Death

- Unwillingness to participate in study specified follow up (including phone contact)
- If the physician deems it is no longer in the best interest of the patient to remain on study

Note: As the objective of this study is overall survival, every attempt will be made to follow patients for life.

Patients will be officially taken off study by contacting the CRO.

3.11.Measurement of Health Related Quality of Life

Baseline Quality of Life Questionnaires (QOL) will be completed prior to randomization, prior to cycle 9 of chemotherapy and then every 12 weeks (+/- 2 weeks) for the first 2 years, every 6 months for the next 3 years, and yearly thereafter. (Note: patients who begin chemotherapy >5 weeks following randomization will be asked to complete the QOL prior to the first cycle of chemotherapy.

Patients will be informed of the details of the QOL part of this study and reassured that their decision to participate will not affect their participation in the either of the treatment arms of this protocol. Once enrolled, the patient has the right at any time to elect not to continue completing the questionnaires. In the event a patient goes off study prior to completion of the follow up time points, the data gathered from their completed QOL questionnaires will be included in the final analysis.

To QOL parameters and quality of life adjusted survival between the two study groups, we will use tools specifically developed for assessment of QOL in gastric cancer patients: FACT-Ga, ; Blazeby JM, Eur J cancer 2004 (Appendix 6). Measures will be initially administered by the Associate Investigator Research Nurse or designee prior to randomization. The Research Nurse will assess the patient's ability to read, and if the patient is unable to read, it will not be administered. The Research Nurse or designee will administer the questionnaires providing a firm surface at a table or a clipboard and a pencil. The patients will be directed to complete the questionnaires using the following instructions:

We would like to better understand how you and other persons in this study feel, how well you are able to do your usual activities, and how you rate your health while you are participating in this research study. To help us better understand these things about you and other persons participating in this study, please complete these two questionnaires about your quality of life. Both questionnaires should not take longer than 15 minutes to complete.

The questionnaires are simple to fill out. Be sure to read the instructions on the top of each questionnaire. Remember, this is not a test and there are no right or wrong answers. Choose the response that best represents the way you feel. I will quickly review the questionnaires when you are done to make sure that all the items have been completed. Please answer all the items with the response that is most applicable.

You should answer these questions by yourself. Your husband/wife or other family members or friends should NOT assist you in completing the questionnaires. Please fill out the questionnaires now. Return the questionnaires to me when you have completed them. We will be asking you to complete these again during some of your follow up visits. If you have any questions, please ask.

Once the patient has completed the questionnaires, the Research Nurse or designee, will review them for completeness and thank the patient for their cooperation. Subsequent measurements will be administered by the Associate Investigator Research Nurse, or designee, when the patient returns for follow-up visits as specified in section 3.9.

The Research Nurse or designee will request that the patient complete the questionnaires prior to seeing the physician, as the interaction between the patient and physician may influence the patient's answers to the questionnaires. In the event a patient is taken off study, patients will be asked to complete one last set of questionnaires (as appropriate to the point of withdrawal) and the data will be included in the analysis. Patients who are only being followed for length of survival will be asked to continue to participate in completing the measures at the set intervals (every 6-12 months) through the mail. Patients will be phoned prior to the scheduled date of measurement and asked to complete the questionnaire; the FACT-Ga will then be mailed to the patient with a self-addressed return envelope and a cover letter with the script above as directions. If the questionnaires are not returned within 2 weeks, patients are phoned again.

4. Supportive Care:

During the post-operative period patients will receive all standard of care supportive measures including nasogastric tube drainage and bowel rest for ileus, pulmonary toilet teaching and incentive spirometry to prevent atelectasis, transfusions, and antibiotics as indicated.

During the administration of systemic chemotherapy patients will receive all necessary supportive care as per the guidelines of the treating physician and institution. This may include:

- Blood transfusions and growth factor support as necessary for the management of myelosuppression. Filgrastim 5 mcg/kg/day subcutaneously may be administered for ANC less than 1000 mm³ or as per the guidelines of the treating institution. **Note:** Filgrastim will not be administered prophylactically during systemic chemotherapy.
- Neutropenic fever will be treated with broad-spectrum antibiotics pending culture results.
- Renal dysfunction (very rare) from oxaliplatin will be managed with supportive measures such as avoidance of renal toxic drugs, maintenance of good renal perfusion (hydration), and diuretics as necessary.
- Diarrhea will be managed with medication such as diphenoxylate/atropine or loperamide.

- Mucositis will be treated with bicarbonate rinses or anesthetic mouth wash.
- Premedication with antiemetics, including 5-HT3 blockers with or without dexamethasone, is recommended during systemic chemotherapy.

5. **Data Collection and Evaluation:**

5.1. **Data Collection**

Data will be collected using the NCI C3D web based data collection system. Quality of life will be assessed using questionnaires as specified in section 3.11.

5.2. **Response Criteria**

5.2.1. **Surgery + chemotherapy arm**

Because of the nature of peritoneal imaging and because cytoreductive surgery will likely eliminate all imageable disease, response can only be measured in terms of radiographic or symptomatic disease-free survival and overall survival. Patients will be followed with CT scans at predetermined intervals as described in Section 3.9. At any time point when there is evidence of progressive disease (imageable tumor nodules or increasing ascites persistent on CT scans as interpreted by the official interpretation of the imaging studies) the patients will be scored as progressive disease. In some cases this may require successive scans, but the time of recurrence will be retrospectively defined at the point the first scan demonstrated imageable disease. Patients who have symptoms of peritoneal tumor recurrence will be followed closely with serial scans and where necessary, laparoscopy (GYMS arm) in order to confirm disease status.

5.2.2. **Systemic chemotherapy alone arm**

Lesions will be evaluated using the RECIST criteria as described below.

Evaluation of target lesions*

- Complete Response (CR): Disappearance of all target lesions
- Partial Response (PR): At least a 30% decrease in the sum of the longest diameter (LD) of target lesions taking as reference the baseline sum LD.
- Progression (PD): At least a 20% increase in the sum of LD of target lesions taking as reference the smallest sum LD recorded since the treatment started or the appearance of one or more new lesions.
- Stable Disease (SD): Neither sufficient shrinkage to qualify for PR nor sufficient increase to qualify for PD taking as references the smallest sum LD.

* All measurable lesions up to a maximum of 10 lesions representative of all involved organs should be identified as **target lesions** and recorded and measured at baseline. Target lesions should be selected on the basis of their size (lesions with the longest diameter) and their suitability for accurate repetitive measurements (either by imaging techniques or clinically). A sum of the longest diameter (LD) for all target lesions will be calculated and reported as the baseline sum LD. The baseline sum LD will be used as reference to further characterize the objective tumor response of the measurable dimension of the disease.

Evaluation of non-target lesions**

- Complete Response (CR): Disappearance of all non-target lesions and normalization of tumor marker level.
- Non-Complete Response: Persistence of one or more non-target lesions
- Progression (PD): Appearance of one or more new lesions. Unequivocal progression of existing non-target lesions

** All other lesions (or sites of disease) should be identified as **non-target lesions** and should also be recorded at baseline. Measurements are not required, and these lesions should be followed as “present” or “absent.”

Evaluation of best overall response

The best overall response is the best response recorded from the start of the treatment until disease progression/recurrence (taking as reference for progressive disease the smallest measurements recorded since the treatment started). The patient's best response assignment will depend on the achievement of both measurement and confirmation criteria.

Target Lesions	Non-Target Lesions	New Lesions	Overall Response
CR	CR	No	CR
CR	Non-CR/Non-PD	No	PR
PR	Non-PD	No	PR
SD	Non-PD	No	SD
PD	Any	Yes or No	PD
Any	PD	Yes or No	PD
Any	Any	Yes	PD

Confirmatory Measurement/Duration of Response Confirmation

To be assigned a status of PR or CR, changes in tumor measurements must be confirmed by repeat studies that should be performed at least 4 weeks after the criteria for response are first met. In the case of SD, follow-up measurements must have met the SD criteria at least once after study entry at a minimum interval of 6-8 weeks.

Duration of Overall Response

The duration of overall response is measured from the time measurement criteria are met for CR/PR (whichever is first recorded) until the first date that recurrent or progressive disease is objectively documented (taking as reference for progressive disease the smallest measurements recorded since the treatment started).

The duration of overall CR is measured from the time measurement criteria are first met for CR until the first date that recurrent disease is objectively documented.

Duration of Stable Disease

Stable disease is measured from the start of the treatment until the criteria for progression are met, taking as reference the smallest measurements recorded since the treatment started.

